Treatment with the PCSK9 inhibitor, evolocumab has been shown by intravascular ultrasound to be associated with a reduction of percent atheroma volume after 1.5 years of treatment; however, it is not known how evolocumab affects specific coronary plaque types and plaque inflammation [6, 7]. Although intravascular ultrasound (IVUS) can provide quantitative measurements of total atheroma volume, it is an invasive technique with associated procedural risks and therefore not practical for routine clinical monitoring of response to medical therapy. Quantitative assessment of changes in plaque burden, plaque composition and vascular inflammation in response to treatment with a PCSK9 inhibitor with noninvasive imaging (CCTA and positron emission tomography (PET) can provide a comprehensive assessment of pathophysiologic changes before and during treatment.

Our group has developed and extensively validated a semiautomatic method of comprehensive measurements of coronary plaque burden and plaque composition in the entire coronary artery tree on CCTA (Autoplaque) [8-12]. Among the many Autoplaque measurements are noncalcified plaque volume, low density non calcified plaque volume, the latter representing the necrotic core. We have shown strong correlation of noncalcified plaque volume with IVUS [10] and have documented excellent reproducibility of the various plaque measurements [12]. In 116 patients having serial studies over 3.5 ± 1.6 years, we have preliminary evidence that a 10% reduction in LDL is associated with an interval reduction in the volumes of all components of non-calcified plaque including adverse plaque characteristics associated with plaque instability and predictive of future cardiac events [13, 14].

With PET, our co-investigators have shown that microcalcification activity within coronary arteries and the aorta-reflecting the rate of deposition of calcium-can be assessed by 18F sodium fluoride

(NaF) PET. This process is considered to be governed by the degree of plaque inflammation, and as such another marker of plaque vulnerability [15]. Thus, 18F NaF PET allows the assessment of the effect of therapy on a measurement related to plaque inflammation.

STUDY DESIGN

This is an early development, single-arm, prospective, open-label study of evolocumab injection in patients with calcified plaque in the coronary artery detected by CCTA. Fifty-five (55) evaluable subjects will be enrolled in the study.

OBJECTIVES

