- Planned coronary revascularization or major non-cardiac surgery in the next 12 months
- Previously or currently on evolocumab
- Specific to beta-blocker administration: hypersensitivity or allergy to metoprolol or other beta-blockers, SBP $<100 \text{ mmHg}$, serious heart problems, such as cardiac failure (hypertension and angina), congestive heart failure, heart block, severe sick sinus syndrome, circulation problems, asthma or other breathing problems, peripheral artery circulatory disorders.

Recruitment and Enrollment

Treatment group

Investigators and/or the study coordinator will perform a weekly review of patients who have had a coronary calcium screening in the past month with coronary artery calcium (CAC), patients who have had a coronary CT angiogram with atherosclerotic plaque, and those who have plaque as documented during invasive angiography in the catheterization lab at Cedars-Sinai Medical Center.

Among these patients, those who meet the inclusion criteria will be recruited to participate. Any information available in the patient's Cedars-Sinai medical records that can help determine eligibility will be viewed. The patient's cardiologist or other medical provider who ordered the CCTA or the invasive angiogram will be approached regarding appropriateness of recruiting the patient. The patient will then be contacted by an investigator or study coordinator for potential consent and participation."

All potential participants will be given enough time to consider the study. It will be explained that their participation is voluntary and will not affect their clinical care should they agree to participate or decline. We will provide a copy of the consent form to patients prior to the day of the study.

The subject's clinical status will be monitored for any adverse change prior to signing informed consent as well as prior to beginning any research procedures.

Feasibility: As of October 2017, we identified from our database 160 patients who have undergone sequential CCTA in whom total cholesterol and LDL values are also known, and who met indications for evolocumab.

DESCRIPTION OF PROCEDURES (Treatment Group)

The study protocol is comprised of a first CCTA (obtained clinically within 90 days prior to enrollment or at the first imaging visit for research purposes) and 18F-NaF PET, treatment with evolocumab for 18 months and a follow up CCTA and 18F-NaF PET.

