18F-NaF PET: According to the package insert, there are no contraindications and no adverse reactions have been reported for Sodium Fluoride F 18 Injection based on a review of the published literature, publicly available reference sources, and adverse drug reaction reporting systems. As with any injectable drug product, allergic reactions and anaphylaxis may occur. This research procedure is being conducted in a clinical setting and emergency resuscitation equipment and personnel are immediately available.

As with other radiopharmaceuticals, this injection has the potential to cause harm to an unborn child. Pregnant women will not be enrolled. Department policy states that all females of child bearing age (10-60yo) are screened to determine pregnancy status. If the female volunteer is of child bearing age and the first day of their last menstrual cycle is not within the past 30 days, we will administer a one-step HCG urine test (QuickVue®, Quidel Corp) in the department to determine their pregnancy status. To minimize the risks to a nursing infant, it is recommended that mothers interrupt nursing for at least 24 hours.

CCTA: The physical procedure of CCTA and administration of intravenous contrast are generally considered low-risk in patients without significant renal dysfunction and other contraindications to intravenous contrast. We will be performing the CCTA at least 48 hours after the initial dye load in the cath lab (if they have been enrolled from the cath lab), the risk of renal dysfunction is minimal.

Beta-Blocker and Nitroglycerin: Administration of metoprolol and sublingual nitroglycerin is associated with minimal risk since patients with clinical contraindications will be excluded.

Radiation: Estimated total radiation exposure from 18F-NaF is approximately 0.81 Rem from the combined 18F-NaF and associated attenuation scans. This calculation is based on 0.0027 Rem/MBq dose equivalent for ¹⁸F-NaF and 0.138 Rem average radiation for cine-CT attenuation scan [22], and approximately 0.8 rem from the coronary CTA.

The study includes a baseline and a final 18F-NaF as well as a baseline and a final CCTA. The baseline CTA may be eligible if done clinically within 60 days prior to enrollment.

Evolocumab:

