Hypersensitivity reactions (e.g., rash, urticaria) have been reported in patients treated with evolocumab, including some that led to discontinuation of therapy. If signs or symptoms of serious allergic reactions occur, discontinue treatment with evolocumab, treat according to the standard of care, and monitor until signs and symptoms resolve. Please see section 6 of the appendix [Repatha prescribing information.pdf](#).

PRIMARY ENDPOINT

1. Change in noncalcified coronary artery plaque volume from baseline to month 18 of treatment with Evolocumab.
2. Change in plaque composition (low density non-calcified and calcified) from baseline to month 18 of treatment with Evolocumab.

STATISTICAL ANALYSIS PLAN

For all statistical analyses, two-sided tests will be conducted and p-values < 0.05 will be considered significant. Continuous variables will be presented as mean \pm standard deviation (SD) or median (interquartile range) as appropriate. Annualized rate of change in total plaque volume, and the volume of non-calcified plaque, specifically, low density non calcified plaque components will be analyzed. Mean values will be compared using a paired Student's t-test median values will be compared using the Wilcoxon rank-sum (Mann-Whitney) test. The relationship between decrease in LDL and changes in plaque volume and individual plaque components per year will be evaluated after adjusting for the effects of confounding variables including age, diabetes, hypertension, smoking, family history of premature coronary artery disease, statin use, baseline LDL and baseline plaque volume. Reproducibility of measurements of, volume of plaque components and total plaque volume will be assessed using intra-class correlations and coefficients of variation.

SAMPLE SIZE POWER CALCULATIONS

In a study of 116 patients who underwent sequential CTA, we observed a reduction in total plaque volume and NCPV among patients who experienced a reduction in LDL of >10% of their baseline LDL level under the influence of statins alone. Based on this preliminary work, we expect to detect a difference of at least 50mm³/year in non-calcified plaque volume (Δ NCPV = NCPV_{pre-treatment} – NCPV_{post-treatment}) among patients who were treated with evolocumab. From our data, we estimate the population standard deviation for measurement of (Δ NCPV/year) to be 115mm³. Using a paired t-test with a power of 80% and an alpha value of 0.05, we would need 44 patients in our treatment group.

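### Does the 80% power fail because the SD of 115 mm³/year may come from scans about 3.5 years apart rather than 18 months?

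*Combined protocol and SAP*

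**What the plan says.** Under Sample Size Power Calculations, the plan begins with earlier work: "In a study of 116 patients who underwent sequential CTA". From that work it takes the target effect: "we expect to detect a difference of at least" 50 mm³/year. It then gives the SD of annualized change as 115 mm³ ("From our data, we estimate the population standard deviation for measurement of" that quantity). With a paired t-test, alpha 0.05 and 80% power it arrives at 44 patients, and it enrols 55 to allow for about 10 withdrawals.

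The scan interval of the earlier series appears only in the background: "In 116 patients having serial studies over 3.5" ± 1.6 years. A second in-house set is mentioned under Recruitment and Enrollment as a feasibility count: "we identified from our database 160 patients who have undergone sequential CCTA".

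The trial's own interval is set under Description of Procedures: "treatment with evolocumab for 18 months and a follow up CCTA". The baseline scan may predate enrolment ("obtained clinically within 90 days prior to enrollment or at the first imaging visit"), although the Risks section gives a shorter window: "The baseline CTA may be eligible if done clinically within 60 days prior to enrollment". The Statistical Analysis Plan analyses annualized rates of change. Nowhere is the SD said to have been adjusted to an 18-month interval.

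**The concern.** An SD per year looks free of the interval, but it is not. Each change is the difference of two scans, each measured with error, divided by elapsed time. Halving the interval doubles the contribution of scan error to the SD of the annualized rate. A figure estimated mostly from scans three or four years apart could therefore be too small for scans 18 months apart.

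The design has almost no slack, because 44 was chosen to just reach 80%. A small rise in the SD takes power below the stated level. In a single-arm study a non-significant result would be read against the stated detectable difference of 50 mm³/year, so a reader would want to know that this difference was realistic.

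**Working it through.** **Inputs from the documents.** Difference 50 mm³/year, SD 115 mm³/year, two-sided alpha 0.05, n = 44 (Sample Size section and SAP). Source interval 3.5 ± 1.6 years (background), if the 116-patient series is the source. Trial interval 1.5 years, or about 1.75 years if the baseline scan is 90 days old.

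**Step 1: reproduce the plan's figure.** The paired t-test is a one-sample t-test on the change, with noncentrality (50/115) × √44 = 2.88 on 43 degrees of freedom. Power is 80.5%, and 44 is the smallest n that reaches 80%. With 45 patients (55 − 10) power is 81.4%; with 55 it is 88.6%.

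**Step 2: slack.** Solving for the SD that gives exactly 80% power: 115.7 at n = 44, 117.1 at n = 45, 130.0 at n = 55.

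**Step 3: how the SD moves with the interval.** For scans T years apart,

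Var(annualized change) = (variance of true rates) + 2 × (scan-error variance)/T².

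Let f be the share of 115² due to scan error in the source; the documents do not give it. Moving to trial interval T,

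SD(T) = 115 × √[(1 − f) + f × R], with R = (1/T²) / E[1/T²] over the source intervals.

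Everything depends on E[1/T²], which is driven by the shortest source intervals. A mean of 3.5 and an SD of 1.6 do not fix it. The distributions below all match that mean and SD; their shapes are assumptions.

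| Source intervals (assumed) | E[1/T²] | R at 1.5 y | Power at 1.5 y, f = 5% / 10% | R at 1.75 y | Power at 1.75 y, f = 5% / 10% |
|---|---|---|---|---|---|
| Lognormal | 0.144 | 3.08 | 76.5 / 72.7% | 2.26 | 78.1 / 75.7% |
| Gamma | 0.177 | 2.51 | 77.6 / 74.8% | 1.84 | 78.9 / 77.3% |
| Uniform | 0.219 | 2.03 | 78.5 / 76.6% | 1.49 | 79.5 / 78.6% |
| Normal cut at 0.5 y | 0.225 | 1.98 | 78.6 / 76.8% | 1.45 | 79.6 / 78.7% |
| Normal cut at 0.25 y | 0.315 | 1.41 | 79.7 / 78.9% | 1.04 | 80.4 / 80.3% |
| Normal cut at 0.2 y | 0.355 | 1.25 | 80.0 / 79.5% | 0.92 | 80.6 / 80.8% |
| Normal cut at 0.1 y (less plausible) | 0.541 | 0.82 | 80.8 / 81.2% | 0.60 | 81.3 / 82.0% |

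Worked example, gamma, f = 10%, 1.5 years: SD = 115 × √(0.90 + 0.10 × 2.51) = 115 × √1.151 = 123.4, giving 74.8% power at n = 44.

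The worst case for a given f has every source pair exactly 3.5 years apart. Then R = (3.5/1.5)² = 5.44, and f = 10% gives SD 138.2 and 65% power. The reported spread of 1.6 years rules that case out.

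Where R is above 1 the SD rises, and where it is below 1 the SD falls. Both are compatible with what the documents report.

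**Step 4: compare with ordinary uncertainty in a planning SD.** If 115 was estimated from 116 patients (115 degrees of freedom, normality assumed), its 95% interval is 115 × √(115/146.6) to 115 × √(115/87.2), about 102 to 132. At n = 44 that corresponds to 89% down to 69% power. The 73–80% in the first five rows at 18 months lies inside that range.

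**Step 5: factors working the other way.** At f = 10% and 1.5 years, those same five rows give 82–87% if all 55 enrolled patients are analysed, or 80–86% at n = 44 if the true effect is 55 rather than 50 mm³/year. The trial also repeats the baseline acquisition protocol at follow-up and reads the two scans together with dates masked. That could make its scan error smaller than in the earlier series.

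**The case for a change.** The strongest argument for acting is that the plan makes one specific claim: 80% power at 50 mm³/year with 44 patients. Extra patients or a larger effect would support a different claim. The break-even is tight: under the first five shapes at 18 months, a scan-error share of only 0.6–3.0% takes power below 80%. The plan itself intends to assess reproducibility, so it does not treat scan error as zero. Stating the source would cost one sentence.

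Part of this stands. The dataset, subgroup and interval behind 115 are not spelled out, and the interval dependence is real. But the order of the sentences points fairly clearly to the 116-patient series, whose interval is given in the background; the 160 patients are offered as evidence of feasibility, not as the source of an SD. The tight break-even only shows that n was set at the smallest value reaching 80%, which is normal practice. The claim that 80% holds only with negligible scan error does not stand: lower scan error in this trial, or enough short intervals in the source, would also preserve it.

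Re-estimating the SD would bring little. When a model with a constant plus a 1/T² term is fitted to 116 simulated pairs with gamma-distributed intervals, the 18-month SD ranges over about 101–150 with no scan error and 101–156 with a 10% share. Such a fit could not tell a problem from its absence.

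**Conclusion.** The concern does not call for a change. The stated 44 and 80% reproduce exactly on the plan's inputs. What remains is a thinly described source for one input, which a reader can largely fill from the background section.

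Assuming the 116-patient series is the source and scan error accounts for 5–10% of its variance, power at 44 patients and 18 months is about 73–80% under five of the distributions tried and about 80–81% under the two with the shortest source intervals. At 21 months the corresponding ranges are about 76–80% and 81–82%. The documents give neither the error share nor the shape of the intervals, so they settle neither the size nor the direction of a shift. The possible loss is no larger than the uncertainty any SD from 116 patients carries.

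The endpoint, the test, the sample size and the conduct of the trial would be the same whichever way the SD moved. The differing 60- and 90-day baseline windows change the interval by about a month at most and do not alter this conclusion.
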